#### INTRODUCTION

The 'Driving Pressure During General Anesthesia for Open Abdominal Surgery' randomized clinical trial (DESIGNATION) compares an intraoperative ventilation strategy with individualized high positive end–expiratory pressure (PEEP) with recruitment maneuvers ('individualized high PEEP') to a conventional strategy with standard PEEP of 5 cmH2O without recruitment maneuvers ('low PEEP'). The primary objective of this study is to determine whether 'individualized high PEEP' is superior to a 'low PEEP' with regard to the incidence of postoperative pulmonary complications (PPC). Enrollment of patients in DESIGNATION already started and the study is planned to finish around the second trimester of 2024.

To prevent outcome reporting bias and data–driven analysis results, the International Conference on Harmonization of Good Clinical Practice (ICH–GCP) recommends that clinical trials should be analyzed according to a pre–specified detailed Statistical Analysis Plan (SAP).

This document presents the updated and finalized SAP of the DESIGNATION trial.

#### METHODS

#### Design, ethics and registration

DESIGNATION is an international, multicenter, parallel, two–group, prospective, randomized, patient and outcome–assessor blinded superiority clinical trial designed to determine if an individualized intra–operative high PEEP strategy guided by the driving pressure ( $\Delta P$ ) is superior to a standard low PEEP strategy with respect to the development of PPC in adult patients that are at risk for PPC and submitted to open abdominal surgery.

The protocol, with a detailed description of the study population, the two strategies and follow–up plan of the DESIGNATION trial was published elsewhere. The DESIGNATION trial was approved by the Institutional Review Board of the Amsterdam University Medical Centers, location Academic Medical Center, in Amsterdam, The Netherlands (2018\_319, February 7, 2019) and is registered with clinicaltrials.gov (NCT03884543).

#### Randomization and blinding

Eligible patients are randomly allocated in a 1:1 ratio to the 'individualized high PEEP' or 'low PEEP' strategy. The allocation sequence is computer–generated by an independent investigator using permuted blocks of different block sizes, with a maximum block size of eight and stratified per center and BMI ( $\leq$  30 vs. > 30 kg/m^2). Randomization is performed by local investigators patient–by–patient employing a dedicated, password protected, SSL–encrypted website.

At each site, at least two investigators are involved with the study. One investigator randomizes the patients immediately before surgery and is responsible for the trial intervention and data collection. A second investigator remains blinded for the randomization and is responsible for postoperative data

collection. The surgeon and patient are kept blind to the allocated ventilation strategy. Since PEEP can be adjusted at any time point upon the surgeons' request or because of concerns about patient's safety, and since patients do not profit from knowing to which group they are allocated to, unblinding is not applicable.

#### Outcomes

The primary study outcome is a collapsed composite of PPC developing within the first five postoperative days. This endpoint follows the European Perioperative Clinical Outcome (EPCO) definition and has been used before in several studies. Patients who develop a least one complication are considered as meeting the primary outcome. The components of the composite outcome of PPC have been defined elsewhere, 1 and these include: 1) severe respiratory failure; 2) bronchospasm; 3) suspected pulmonary infection; 4) new pulmonary infiltrates; 5) aspiration pneumonitis; 6) new atelectasis; 7) acute respiratory distress syndrome (ARDS); 8) new pleural effusion; 9) new cardiopulmonary edema; and 10) new pneumothorax. The selected PPC can sensibly be added together as they share common pathophysiological mechanisms and have plausibility to be affected in the same direction by the intervention to be tested in this study. If pulmonary infiltrates, pleural effusion, atelectasis, cardiopulmonary edema or pneumothorax are already present in any preoperative chest imaging and did not worsen, the patient will not be coded as a new complication in the postoperative period if present.

Secondary outcomes also have been defined elsewhere, and include: 1) mild respiratory failure; 2) a composite outcome of intraoperative complications, including desaturation, hypotension, any need for vasoactive agents, and any

new arrhythmias; 3) postoperative extrapulmonary complications; 4) intraoperative fluid balance; 5) impaired wound healing; 6) unplanned admission to an ICU; 7) length of intensive care unit (ICU) stay (if applicable); 8) length of hospital stay; and 9) all–cause hospital mortality. All definitions are available in **Table 1**.

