#### Secondary outcomes

For binary outcomes, the effect of 'individualized high PEEP' compared to 'low PEEP' on the incidence of PPC will be assessed using a mixed–effect generalized linear model with binomial distribution and identity link, with sites included as random effects to account for the clustering effect and reported as absolute difference with a two–sided 95% confidence interval. For continuous outcomes, the comparison will be made using a mixed-effect median regression with sites also including as clustering effect, and reported as median difference with a two–sided 95% confidence interval as median difference with a two–sided 95% confidence as median difference with a two–sided 95% confidence interval. In addition, a Holm–Bonferroni correction to control the family–wide error rate to the *p* values for all 17 secondary outcomes will be done and presented in a Table.

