#### Subgroup analysis

Treatment effects on incidence of PPC will be analyzed according to the following predefined subgroups: 1) age < 65 years  $vs \ge 65$  years; 2) body mass index < 30 kg/m^2 vs BMI  $\ge$  30 kg/m^2; 3) baseline SpO2 < 96% vs SpO2  $\ge$  96%; 4) moderate vs high risk for PPC according to the ARISCAT risk score (< 45 vs.  $\ge$  45); 5) duration of surgery < 3 hours  $vs \ge$  3 hours; and 6) planned destination to ICU or HDU vs ward. Analyses of heterogeneity of effects across subgroups will be performed with the use of treatment–by–subgroup term added to the primary model and will be presented in a forest plot.

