# Table 2 – List of proposed tables and figures

|               | Description   |
|---------------|---|
| Main paper    |   |
| Table 1       | Baseline Characteristics of the Included Patients   |
| Table 2       | Ventilation and Intraoperative Characteristics  |
| Table 3       | Primary and Secondary Outcomes  |
| Figure 1      | Participant Flow Diagram  |
| Figure 2      | Postoperative Pulmonary Complications in Prespecified Subgroups
A forest plot showing the absolute difference and two-sided 95% confidence intervals with p value for interaction calculated via a test for treatment-by-subgroup interaction in
the regression model. A solid line of reference in the number 1 and a dashed line of reference in the overall effect will be shown.  |
| Online Supple | ement   |
| eTable 1      | Rate of Missing Data A table showing the rate of missing data.  |
| eTable 2      | Additional Intraoperative Characteristics
A table showing additional intraoperative characteristics.   |
| eTable 3      | Rescue Therapies in Included Patients
A table showing the steps of rescue therapies in patients receiving rescue in each arm.  |
| eTable 4      | Protocol Deviations
A table reporting the protocol deviations in each arm.   |
| eTable 5      | Daily Assessment of Included Patients
A table showing characteristics over the first 5 days of follow-up.  |
| eTable 6      | Multiplicity adjustment for secondary outcome analyses
A table showing the observed p values for all the secondary outcomes and ordered from the lower until the higher and the corrected p values using a Holm–Bonferroni correction  |
| eTable 7      | Sensitivity Analyses for the Primary Outcome
A table showing the proposed sensitivity analyses for the primary outcome (count analysis, common effect test, average relative effect test and heterogeneity of treatment effect)  |

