| Desaturation   |  |                       |                                 |         |
| Hypotension  |  |                       |                                 |         |
| Need for vasoactive agents                           |  |                       |                                 |         |
| New arrhythmias                                      |  |                       |                                 |         |
| Postoperative extrapulmonary complications – no. (%) |  |                       |                                 |         |
| Sepsis   |  |                       |                                 |         |
| Septic shock   |  |                       |                                 |         |
| Extrapulmonary infection                             |  |                       |                                 |         |

Anastomotic leakage Acute kidney injury Intraoperative fluid balance – no. (%) Impaired wound healing – no. (%) Unplanned admission to intensive care unit – no. (%) Intensive care unit length of stay, days Hospital length of stay, days All-cause hospital mortality – no. (%)

Data are median (quartile 25th - quartile 75th) or N / total (%). Abbreviations: PEEP is positive end-expiratory pressure.

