# MODIFICATIONS FROM THE ORIGINAL ANALYSIS PLAN

| ANALYSIS  | ORIGINAL PLAN
( TRIALS 2020; 21:198)   | UPDATE IN THE SAP
(Closed in January 12, 2024)  | INCLUDED IN THE NEW SAP
(Updated in January 12, 2025) |
|---|--|--|--|
| Model for the primary outcome                   | Risk ratio and 95% confidence intervals calculated with Wald's likelihood ratio approximation test and with $\chi^2$ tests for hypothesis testing.   | Mixed-effect generalized linear model with binomial
distribution and identity link, with sites included as random
effects to account for the clustering effect and reported as
absolute difference with a two–sided 95% confidence
interval. |  |
| Model for binary secondary outcomes             | Risk ratio and 95% confidence intervals calculated with Wald's likelihood ratio approximation test and with $\chi^2$ tests for hypothesis testing.   | Mixed-effect generalized linear model with binomial
distribution and identity link, with sites included as random
effects to account for the clustering effect and reported as
absolute difference with a two–sided 95% confidence
interval. |  |
| Model for ICU and
hospital length of
stay | Generalized linear models considering distributions
that will fit a possible heavy right-tailed distribution
without zero (such as truncated Poisson, gamma
distribution, or inverse Gaussian), choosing the best
fit according to the model's deviance. | Mixed-effect median regression with sites also including
as clustering effect, and reported as median difference
with a two–sided 95% confidence interval.   |  |
| Time-to-event
analyses                       | Kaplan–Meier curves will be used to report time to
postoperative pulmonary complications, and hazard
ratios with a 95% confidence interval will be
calculated with Cox proportional hazard models
without adjustment for covariates.                     | No time-to-event analysis planned to be performed.   |  |

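### ICU length of stay would in effect be tested only among patients admitted to an ICU, a group the treatment can change, so its p value and interval do not compare randomised groups

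*SAP*

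**What the plan says.** The SAP's Outcomes section lists "length of intensive care unit (ICU) stay (if applicable") among the secondary outcomes, directly after unplanned ICU admission. It does not say what value, if any, a never-admitted patient receives.

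For continuous outcomes, the Secondary outcomes section states that "the comparison will be made using a mixed-effect median regression with sites also including as clustering effect", reported as a median difference with a 95% interval. Statistical analyses adds a two-sided test at 0.05 for every secondary outcome. The Holm–Bonferroni correction is to cover the p "values for all 17 secondary outcomes will be done and presented in a Table", and the planned supplementary table is described as "A table showing the observed p values for all the secondary outcomes".

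Table 7 has the rows "Unplanned admission to intensive care unit" and "Intensive care unit length of stay, days" under the same full-arm columns, with an absolute difference, interval and p value. Neither row is marked as conditional or descriptive. Planned ICU or HDU care is known for each patient, since Subgroup analysis uses "planned destination to ICU or HDU vs ward", but that subgrouping is applied to PPC only.

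**The concern.** If only admitted patients contribute, the analysis conditions on an event after randomisation. Part of the admitted group got there through unplanned admission, which the trial itself tests as a possible treatment effect. Keeping patients in their assigned arm does not help, because those without an ICU stay supply no value.

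The median among the admitted can then move either way simply because treatment changed who was admitted. Preventing brief unplanned stays can leave a longer-staying group behind, so a benefit can look like harm. With an interval, a p value and a multiplicity adjustment, the row will be read as an effect of treatment on length of stay.

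**Working it through.** **Which patients are analysed.** Two readings are possible.

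1. *Admitted patients only.* The words in brackets after the outcome point this way, and no zero-day rule is given. The modifications table supports it: the superseded model for ICU and hospital stay was for distributions "without zero (such as truncated Poisson, gamma" and similar. That text is historical and is only supporting evidence.
2. *All patients, with 0 for no ICU.* If under half of an arm is admitted, more than half of its values are 0 and its median is 0. With 32% admitted, for example, 68% of values are 0. The planned median difference is then 0 − 0 = 0, whatever happens to the admitted.

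**Inputs from the SAP.** 734 per arm and 2% dropout, so 734 × 0.98 = 719 analysed per arm. The sample size itself reproduces: 34% against 27.2% with 80% power needs 720 per arm, and 720/0.98 = 735, or 1,470 in total against the stated 1,468. The SAP has no figure for ICU admission or stay.

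**Assumed inputs.** Control arm: 15% planned, 10% short unplanned and 7% long unplanned admissions. Stays are log-normal with log-SD 0.6, and the long-stay median is 5 days. Planned/short medians are varied as 2/1, 2/2, 1/1 and 1/2 days. Treatment changes only the admission fractions, never a patient's stay.

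**Formula.** The admitted-only median x solves Σ wₖ Φ(ln(x/mₖ)/0.6) / Σ wₖ = 0.5, where wₖ are the admission fractions and mₖ the medians.

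For planned/short 2/1:
- Control, x = 1.91: (0.15 × 0.469 + 0.10 × 0.859 + 0.07 × 0.054)/0.32 = 0.160/0.32 = 0.50.
- Short stays halved, x = 2.19: (0.15 × 0.560 + 0.05 × 0.904 + 0.07 × 0.084)/0.27 = 0.135/0.27 = 0.50.
- Shift: 2.19 − 1.91 = +0.28 day. ICU days per randomised patient are proportional to Σ wₖmₖ, which falls from 0.75 to 0.70, or 7%. Total ICU use falls while the tested median rises.

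| Planned/short median (days) | 2/1 | 2/2 | 1/1 | 1/2 |
|---|---|---|---|---|
| Control median, admitted only | 1.91 | 2.37 | 1.23 | 1.66 |
| Shift, short halved (ICU days per patient fall 7–14%) | +0.28 | +0.09 | +0.07 | −0.09 |
| Shift, short and long halved (fall 30–39%) | +0.04 | −0.14 | −0.095 | −0.30 |
| Shift, long halved (fall 21–29%) | −0.20 | −0.18 | −0.12 | −0.18 |
| Shift, short increased by half | −0.19 | −0.06 | −0.04 | +0.06 |
| Wrong-direction p<0.05, short halved | 26% | 7% | 7% | 1% |
| Same, at 0.05/17 | 5% | 1% | 1% | 0% |
| Wrong-direction p<0.05, short cut by 20% | 7% | 4% | 3% | 3% |

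With 20% reductions of any kind, all shifts lie between −0.11 and +0.10 day, and wrong-direction significance at 0.05/17 is under 1%.

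The rejection rates come from 3,000 simulated trials per setting, using a median-difference z test among the admitted with no site effect. This approximates the planned mixed-effect model and is not identical to it. With no effect, each tail rejects in 2.2% to 2.5%. An order-statistic standard error gives similar rates with short stays halved: 23–25%, 5–6%, 4–6%, and 1% or less.

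**Sensitivity, short stays halved.** For log-SD 0.4 to 0.8 the shifts are +0.27 to +0.28, +0.08 to +0.09, +0.05 to +0.08 and −0.13 to −0.07 day. Varying planned admission over 5–30% and short admission over 5–10% as well gives +0.08 to +0.65, +0.02 to +0.29, +0.01 to +0.48 and −0.13 to +0.26.

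**The case against.** The SAP nowhere says that never-admitted patients are excluded. It refers to the published protocol for secondary-outcome definitions, so a rule may exist there. The superseded model covered hospital stay too, which is rarely zero. The complete-case rule concerns missing data and does not say that a never-admitted patient counts as missing. The exclusion is indeed inferred. But the main alternative, a zero for no ICU stay, fails with a median regression unless at least half of an arm is admitted, so a zero-day rule in the protocol would not rescue the method stated here.

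On size, the objection largely stands. The trial is planned for a 20% relative reduction in PPC. If admissions fell by a similar proportion, the distortion would be small, and often in the beneficial direction. The 26% figure needs short unplanned stays to be halved, long ones to be untouched, and planned stays to last longer than short unplanned ones. Unplanned admission and mortality also sit in the same table, so a careful reader can see much of what is happening.

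Membership of the Holm family is not certain either. The SAP says 17, while Table 7 shows 18 secondary rows counting composites and their components, and which 17 are meant is not stated.

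**Conclusion.** The concern holds. As the plan most naturally reads, ICU stay receives a hypothesis test in a group formed after randomisation and partly defined by another tested outcome. Scoring the never-admitted as 0 would make the same test uninformative unless at least half of an arm is admitted. This does not depend on the assumed numbers.

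The size and sign of any distortion do depend on them, and the SAP gives no basis for fixing them. A significant result in the wrong direction needs a large, selective effect and rarely survives at 0.05/17. The point concerns one secondary outcome and leaves the primary analysis untouched. It merits correction because the row would be presented as a treatment effect and the repair is cheap.

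**What to change.** In Outcomes, Secondary outcomes and Table 7, report ICU days among admitted patients descriptively: the number admitted per arm as denominator, with median and interquartile range, no p value and no place in the Holm family. State that the row is to be read beside unplanned ICU admission and hospital mortality. Adjust the Holm count in Secondary outcomes and eTable 6, and log the change in the modifications table.

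If a tested comparison is wanted, define it in all randomised patients, with 0 for no ICU stay and a pre-stated rule for deaths, and use a rank-based or ordinal method.

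The cost is SAP wording; no new data are needed. ICU stay loses its test. If it is one of the 17, the first Holm step moves from 0.05/17 = 0.0029 to 0.05/16 = 0.0031.

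The optional all-patient test would not be in days, would overlap with the admission and mortality outcomes, and offers no gain in power. Under the assumptions above, the existing unplanned-admission row detects halving of short stays in 76–78% of trials at p<0.05, against 41–56% for a rank test in all randomised patients.

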#### Cleaning and closing of the database

The database will be locked as soon as all data are entered and all discrepant or missing data are resolved, after all efforts are employed to complete the database, and we consider that the remaining issues cannot be fixed. At this step, the data will be reviewed before database locking. After that, the study database will be locked and exported for statistical analysis. At this stage, permission for access to the database will be removed for all investigators, and the database is locked and archived.

#### Missing data

No or minimal losses to follow–up for the primary outcome is anticipated. Complete–case analysis will be carried out for all outcomes. However, if more than 5% of missing data is found for the primary outcome, a sensitivity analysis using multiple imputations and estimating–equation methods will be carried out. Multiple imputation will consider imputation models based on prognostic baseline and post-baseline variables under a missing at random assumption.

#### Sample size

DESIGNATION is designed to enroll a total of 1.468 patients (734 in each arm). This number allows the detection of a reduction in the incidence of the primary outcome from 34% in the control group to 27.2% in the experimental group (relative risk reduction of 20%), considering a type I error of 5%, a power of 80%,

similar allocation ratio between the arms (1:1) and a dropout rate of 2%. The required sample size is calculated based on an estimated effect size derived from individual patient data from previous trials.

#### Statistical analyses

All statistical analyses will be conducted on an intention-to-treat basis, with patients analysed according to their assigned treatment arms, except for cases lost to follow up or withdrawal of informed consent. In addition, a per-protocol analysis will be conducted. Variables will be expressed as counts and percentages, means and standard deviations (SD), or medians and interquartile ranges (IQR) whenever appropriate.

The primary and secondary outcomes will be assessed using a two–sided superiority hypothesis test with a significance level of 0.05 and presented with a two–sided 95% confidence interval. In addition to the unadjusted *p* values for secondary outcomes, a Holm–Bonferroni procedure will be applied to control for multiple testing. Analyses will be performed using the software R (R Core Team, 2016, Vienna, Austria). A list of proposed tables and figures is in **Table 2**.

#### Trial profile

Patient flows will be represented in a CONSORT flowchart (Figure 1).

#### **Baseline characteristics**

A description of the baseline characteristics of the trial participants will be presented by treatment group (**Table 3**). Discrete variables will be summarized as numbers (%). Percentages will be calculated according to the number of trial participants for whom data are available. Where values are missing, the denominator will be stated in the table and no assumptions or imputations will be made. Continuous variables will be summarized by either means and standard

deviations (SD) or medians and interquartile ranges (IQR), according to the observed distribution of the variable.

#### Adherence to study interventions and ventilatory variables

Surgical and perioperative characteristics will be reported (**Tables 4** and **5**). Ventilatory variables and vital signs will be reported after intubation, one hour, and in the last hour of surgery and compared between the two groups. Absolute differences between groups will be calculated using median regression for continuous variables (reported as median difference) and generalized linear models with binomial distribution and an identity link for binary variables (reported as difference in percentages). Plots comparing ventilatory variables and vital signs among the groups during the first three hours of surgery and in the last hour will be constructed (presenting the data as mean and 95% confidence interval in each time point).

